Enrollment:

Local neonatal intensive care unit census will be screened at a minimum of one time per week to determine if there are neonates who potentially meet the enrollment criteria

defined above. The patients' clinical course will be monitored and when the infant requires minimal ventilatory support the parent(s) of said infants will be approached. The study will be explained and consent will be sought. If consent is granted, the infant's medical course will be monitored and once the infant is extubated and stable for a minimum of 48 hours on one of the approved ventilatory modes the routinely obtained morning capillary blood gas will be monitored until the infant meets study entry criteria.

Study Protocol:

Baseline Data Collection:

Demographic data: Patient gestational age at delivery, admission weight, receipt of surfactant administered, age at extubation, time since extubation, current post menstrual age, previous nitric oxide therapy, current nitric oxide therapy, and current weight.

Baseline vitals and ventilation mode: Heart rate, blood pressure, FiO₂, oxygen saturations, transcutaneous partial pressure of carbon dioxide (TCO₂) and current mode of ventilation will be recorded four times in a one minute period and the values averaged to minimize normal variation. Intervention time will be manipulated to begin no later than one hour after the previous feeding, as to minimize interruption of feedings given the typical every 3 hour feeding schedule used in our NICU.

Safety

TCO₂ monitor will be attached to the infant by respiratory therapy staff and the device will be calibrated according to protocol (reference TCO₂ monitor manual). Carbon dioxide diffusion through the skin will be monitored continuously during the intervention (Bromley, 2008) to assess for periods of hypo or hypercarbia.

Edi Catheter placement: Edi catheter size will be selected according to infant's weight and length. It will be inserted according to manufacturer's guidelines and adjustments will be made to optimize positioning (Maquet Critical Care AB). At the time of study initiation and every thirty minutes thereafter TCO₂, heart rate (HR), respiratory rate (RR), minute ventilation, peak Edi, minimum Edi, and PIP will be recorded four times in a one minute period and the values averaged to minimize normal variation. Current NAVA settings, oxygen saturations, FiO₂, and blood pressure (BP) will also be recorded at these times.

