Physician member of the research team will be present at bedside during the entire study intervention.

NAVA settings:

Infants will be maintained on previous level of PEEP or calculated PEEP, rounding up to whole numbers. Initial NAVA level will be determined by starting with an initial NAVA level of 0.5 microvolts/cm of H₂O. The NAVA level will then be adjusted either by increasing or decreasing NAVA level settings by 0.1 microvolts/cm of H₂O to generate a PIP that is a minimum of 8 cm of H₂O greater than the current PEEP. Apnea alarm will be set at 5 seconds, which will initiate the NAVA back up setting if no electrical activity is detected by the Edi catheter. Back up NAVA settings will be set with a PIP of 12 cm of H₂O greater than current PEEP, respiratory rate of 60 breaths per minute (RR) and inspiratory time of 0.5 seconds. Fraction of inspired oxygen (FiO₂) will be adjusted to keep infant's oxygen saturations within previously established clinical parameters.

Infants who are currently receiving respiratory support via NAVA at the time of the study will have their NAVA level increased by 50%, rounding up to the nearest 0.1

microvolts/cm of H₂O. The other NAVA settings will be adjusted as previously described.

Study Intervention Procedure and Data Collection:

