At initiation of intervention, and at time 30, 60, 90, and 120 minutes, TCO₂, heart rate (HR), respiratory rate (RR), minute ventilation, peak Edi, minimum Edi, and PIP will be recorded four times in a one minute period and the values averaged to minimize normal variation. Current NAVA settings, oxygen saturations, FiO₂, and blood pressure (BP) will also be recorded. At 60 minutes of intervention if the TCO₂ average has not decreased by 5 mmHg from baseline or has risen, the current NAVA level will be increased by 50%, and the HR, RR, minute ventilation, peak Edi, minimum Edi, and PIP will be recorded as described above. At 90 minutes if the TCO₂ average has not decreased by 5 mmHg from baseline or has risen; the NAVA level will be increased by 50% from the current level and data collected as describe at 60 minute intervention. At the completion of the study (120 minutes or pCO₂ outside of established limits) the HR, RR, BP, minute ventilation, FiO₂, oxygen saturations, peak Edi, minimum Edi, and PIP will be recorded four times in a one minute period and the values average to minimize normal variation. A capillary blood gas will be obtained according to standard unit protocol with a warmed heel.

If at any time during the study the TCO₂ level is greater than 80 mmHg the nasal pharyngeal tube will be evaluated for patency and exchanged if needed. If TCO₂ levels to do not return to less than 80 mmHg the study will be terminated and management will be deferred to primary medical team. If the TCO₂ level is less than 35 mmHg the infant will exit the study early and heart rate, FiO₂, oxygen saturations, HR, RR, peak Edi, minimum Edi, and PIP will be recorded four times in a one minute period. The values

will be averaged to minimize normal variation. Blood pressure will also be measured. A capillary blood gas will be obtained according to standard unit protocol with a warmed heel.

Statistics

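### The 60- and 90-minute NAVA increases have no lower TCO2 limit, so an infant already within 5 mmHg of the 35 mmHg exit can be given more support

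*Combined protocol and SAP*

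**What the plan says.** All references are to the combined protocol and SAP.

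- **Escalation at 60 minutes** (Study Intervention Procedure and Data Collection): if the TCO2 average "has not decreased by 5 mmHg from baseline or has risen, the current NAVA level will be increased by 50" per cent.
- **Escalation at 90 minutes** (same section): on the same test, "the NAVA level will be increased by 50% from the current level".
- **Low exit** (same section): "If the TCO₂ level is less than 35 mmHg the infant will exit the study early". Final recordings and a capillary gas are then taken.
- **High limit** (same section): "If at any time during the study the TCO₂ level is greater than 80 mmHg", the tube is checked and, if TCO2 stays high, the study stops for that infant.
- **Oversight** (Safety): TCO2 is followed continuously "to assess for periods of hypo or hypercarbia", and "Physician member of the research team will be present at bedside during the entire study intervention".
- **Entry** (Study Population / Eligibility): a capillary gas from the previous 24 hours must show pH below 7.35, pCO2 above 45 mmHg, or both. Under Enrollment, "the routinely obtained morning capillary blood gas will be monitored until the infant meets study entry criteria".

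Neither escalation step carries a lower TCO2 limit, and no text gives the bedside physician authority to withhold one.

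**The concern.** The escalation check asks how far TCO2 has moved. The exit rule asks where TCO2 is. For an infant who starts low, the two conflict: the response that would spare the infant an increase lies beyond the value at which participation ends. Such an infant receives more support although TCO2 is already near the level the protocol treats as too low.

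Low baselines are permitted. Entry on pH alone allows a pCO2 of 45 mmHg or less. The qualifying gas is a routine morning capillary sample, whereas the check uses a transcutaneous baseline recorded for the study, possibly many hours later.

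What is at stake is an avoidable push towards hypocarbia in very low birth weight infants, and a bedside team that would have to depart from the written plan to prevent it.

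**Working it through.** The plan gives no figure to reproduce here, so the check is of the decision rule itself.

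**Inputs.** B is baseline TCO2 and C is the current TCO2 average, both in mmHg. From Study Intervention Procedure and Data Collection: escalate at 60 and 90 minutes if B − C < 5; exit if C < 35; each step multiplies the NAVA level by 1.5.

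**Step 1: can the infant meet the target and stay in the study?** This needs C ≤ B − 5 and C ≥ 35, hence B ≥ 40.

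- For B from 35 to below 40, B − 5 runs from 30 to below 35, so no value of C satisfies both. While the infant remains in the study, B − C ≤ B − 35 < 5, and every check reached leads to an increase. Example: from B = 38 the target is 33, which is past the exit.
- For B of 40 or more, the target can be reached. At B = 40 it is exactly 35.

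**Step 2: when does escalation occur with C below 40, that is, within 5 mmHg of the exit?** It needs B < C + 5, and C < 40 gives B < 45.

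| Baseline | Current | Fall | Escalated? | Room before exit |
|---|---|---|---|---|
| 38 | 36 | 2 | yes | 1 |
| 40 | 36 | 4 | yes | 1 |
| 43 | 39 | 4 | yes | 4 |
| 45 | 39 | 6 | no | 4 |

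For B of 45 or more, any C below 40 is already a fall of more than 5, so the problem does not arise.

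**Step 3: count on whole-mmHg values, C = 35 to 39 and B at least 35.**

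- TCO2 unchanged or lower (C ≤ B, B − C < 5): 5 values of C × 5 values of B = 25 escalating pairs.
  - B below 40: 5 + 4 + 3 + 2 + 1 = 15 pairs, where the target cannot be met without exit.
  - B = 40 to 43: 1 + 2 + 3 + 4 = 10 pairs, where it still could be.
- TCO2 higher but still below 40 (B = 35 to 38): 4 + 3 + 2 + 1 = 10 escalating pairs.
- Total: 25 + 10 = 35.

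These counts describe the rule. They are not frequencies of infants.

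**Step 4: size of the added support.** Two steps give 1.5 × 1.5 = 2.25 times the level before the first check. An infant already on NAVA at entry has a 50% increase at the start (NAVA settings), so the total is 1.5 × 1.5 × 1.5 = 3.375 times the level at entry, before rounding.

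**Step 5: effect of a floor at 40.** A rule that withholds the increase when C < 40 removes escalation in all 35 pairs. Any rise to 40 or above still triggers it: 39 to 60, for instance, is outside the floor.

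**The case against.** The strongest reply is that the design is coherent: raise support until either a response target or a stopping limit is reached. The protocol does act on the current value, through continuous TCO2 monitoring and the exit below 35. Values of 35 to 39 lie inside its limits, and no text treats 40 as a boundary. A physician is present throughout, and the documents do not show that any infant will have such a baseline.

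Much of this stands. Harm is limited, exposure is unknown, and 40 is a reviewer's figure, though built from the protocol's own 35 and 5. But monitoring and exit respond after TCO2 has fallen, and the physician has no written discretion over a step that is worded as mandatory. For baselines of 35 to below 40 the response target cannot be met at all, so the only possible endings are the exit limit or the end of the study.

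Two stronger readings are tempting and not supported.

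- A reader might infer from the preliminary median change of −3.5 mmHg in 24 infants that such escalation will be common. That figure suggests, if TCO2 behaves as capillary pCO2 did, that missing a 5 mmHg fall is common. Baseline values are not given, so it says nothing about infants below 40 mmHg.
- A reader might infer that early exits cost the trial its outcome or its power. The plan counts them as completion, "At the completion of the study (120 minutes or pCO₂ outside of established limits", and takes a capillary gas at that point. The primary measurement is kept.

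**Conclusion.** The point holds as a gap in the intervention rule, not as an error in the analysis. With a baseline TCO2 of 35 to below 40 mmHg, the plan requires more support at each check until exit or the end of the study. With a baseline of 40 to below 45, it can require more support within 5 mmHg of the exit. At 45 or above there is no conflict.

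This assumes that the check is applied as written and that some infants have baselines below 45. The eligibility rules allow that, but the documents do not say how many there will be; the number may be small or zero. With the existing safeguards, this is a modest safety improvement worth making because it is cheap.

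Because pH can qualify an infant while the Statistics section tests only pCO2, a reader might also infer that the analysis is deficient. That is not claimed: choosing pCO2 as the outcome is legitimate. A descriptive summary of the change in pH would be an optional extra.

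**What to change.** Add one sentence to Study Intervention Procedure and Data Collection, after the 90-minute step:

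*At 60 and 90 minutes the NAVA level is not increased if the current TCO2 average is below 40 mmHg.*

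The 40 is the 35 mmHg exit plus the protocol's own 5 mmHg step. No further condition about TCO2 having risen is needed. Such a condition would only keep escalation for rises that end below 40, such as 35 to 36, where 1 mmHg of room remains.

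The cost is slightly less escalation in infants below 40. That includes some with baselines of 40 to below 45 who could still have fallen 5 mmHg without exit (10 of the 35 whole-mmHg pairs), and those with a small rise that stays below 40 (another 10). The loss in the first group seems acceptable, since an infant at 36 is equally close to exit whether the baseline was 38 or 40. No new procedure, measurement or change to the statistical analysis is required.

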This prospective study will look at extubated very low birth weight (VLBW) infants who received surfactant and are stable on their current distending pressures via continuous positive airway pressure (CPAP) or nasal cannula. This is a cross over trial utilizing NAVA to demonstrate that it can improve ventilatory support determined by improved blood gas parameters.

Preliminary Data:

We have retrospectively studied NAVA technology using a noninvasive strategy to provide nasal ventilation. All very low birth weight infants (VLBW) (less than 1500 grams) with respiratory distress syndrome treated with surfactant in our NICU from July 2011 to August 2012 and ventilated with noninvasive nasal NAVA were eligible. The change in partial pressure of carbon dioxide (pCO₂) of VLBW infants who had increased NAVA support in response to a capillary blood gas were studied. The pre- and post-intervention pCO₂ differences were determined for n=24 patients and the differences ranged from a decrease of 16 mmHg to an increase of 5 mmHg with a median value of -3.5 mmHg. This decrease was found to be significant using the Wilcoxon signed-rank test (p<0.001).

Study Design:

Prospective cross-over of NIV NAVA compared to nasal CPAP or high flow nasal cannula respiratory support in VLBW infants with a history of RDS.

Study Population / Eligibility:

- Birth weight was less than 1500 grams with clinical history of respiratory distress syndrome treated with surfactant
- Chronological age greater than or equal to seven days.
- At least 48 hours post-extubation and medically stable as determined by the treating medical team
- On one of the follow modes of mechanical support receiving a distending pressure via nasal pharyngeal tube (NP) or nasal cannula: continuous positive airway pressure (CPAP), intermittent mechanical ventilation (IMV), or neutrally adjusted ventilatory assistance (NAVA).
- Infants may be on high flow nasal cannula if the flow is large enough to provide a positive end expiratory pressure (PEEP) of 6 as defined by $PEEP\ of\ 6 = 0.68 * weight\ (kg) + 0.92$ (Sreenan, Lemke, Hudson-Mason, & Osiovich, 2001)
- Infants will be required to have a capillary blood gas obtained via heel stick after placement of heel warmer within 24 hours of study entry that demonstrates a pH of less than 7.35 and/or a partial pressure of carbon dioxide (pCO₂) greater than 45 mmHg.

Exclusion criteria:

- Severe congenital abnormalities
- Grade III or IV intraventricular hemorrhage.

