Power calculations were performed using a detectable difference in pre-post pCO₂ of 4mmHg based on published findings (Stein & Howard, 2011). Assuming a $\beta=0.2$, a significance level $\alpha=0.05$ and $\sigma=1$, the estimated sample size needed to detect a difference is 35 subjects. To account for possible subject attrition, a total of 40 subjects will be recruited and study data will be collected at the patient's bedside using an electronic data collection form. The pre- and post- intervention capillary pCO₂ will be compared using a paired t-test and testing the null hypothesis that there is no difference in pCO₂ levels. Further analyses will test if the difference is greater than 5mmHg. In the event that distributional assumptions for the t-test are not satisfied in these data, a nonparametric Wilcoxon signed-rank test will be used to compare the pre- and post-measures. Multiple Linear Regression methods allowing for covariate adjustment will be used to determine if any significant associations exist between patient characteristics and the change in pCO₂ levels.

Planned Tables and Figures

Table 1 baseline characteristics

Figure 1 PCO₂ start vs final

Figure 2 TCO₂ vs time

Figure 3 bell shaped curve of delta pCO₂

Figure 4 Nasal Pharyngeal NAVA and RAM-cannula bell shaped curve of delta pCO₂

Table 2 characteristics of patients who failed NAVA therapy in 2 hours (if needed)

Table 3 characteristics of patients who had significant changes in pCO₂ vs those who had no changes (if needed)

Table 4 characteristics of patients who were eligible for the study but declined enrollment

References

- Maquet Critical Care AB, "NAVA and NIC NAVA in neonatal settings", pocket guide, revision 00, 2010.
- Angus, D. C., Linde-Zwirble, W. T., Clermont, G., Griffin, M. F., & Clark, R. H. (2001). Epidemiology of neonatal respiratory failure in the united states: Projections from california and new york. *American Journal of Respiratory and Critical Care Medicine*, 164(7), 1154-1160.
- Attar, M. A., & Donn, S. M. (2002). Mechanisms of ventilator-induced lung injury in premature infants. *Seminars in Neonatology : SN*, 7(5), 353-360.

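### The stated planning inputs (4 mmHg, sigma = 1, alpha 0.05, beta 0.2) give about 3 infants, not 35, and the SD that would give 35 is not reported

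*Combined protocol and SAP*

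**What the plan says.** The sample size rests on one short run of text in the Statistics section. The effect is a "detectable difference in pre-post pCO₂ of 4mmHg based on published findings". The error rates are beta 0.2 and alpha 0.05, and sigma is set to 1 with no unit. The text does not say whether sigma is the SD of the paired difference or of a single measurement. From this the plan concludes that "the estimated sample size needed to detect a difference is 35 subjects", and, to allow for attrition, "a total of 40 subjects will be recruited".

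On the analysis, the pre- and post-"intervention capillary pCO₂ will be compared using a paired t-test", with a Wilcoxon signed-rank test as fallback. Sidedness is not stated; a null hypothesis of no difference suggests two-sided.

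The only information on the spread of pCO₂ changes is under Preliminary Data. In 24 infants "the differences ranged from a decrease of 16 mmHg to an increase of 5 mmHg with a median value of -3.5 mmHg". No SD is given there.

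**The concern.** A 4 mmHg difference against an SD of 1 is an effect of four standard deviations, which a handful of infants would detect. A requirement of 35 implies a much smaller standardised effect, so at least one input as printed is not the one that was used.

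This matters because the passage is the only justification for 35 evaluable and 40 recruited infants. Power depends strongly on the SD of the paired difference, and that is the quantity the reader is not given. The claim of 80% power for 4 mmHg therefore cannot be confirmed, and the reader cannot tell whether the trial is generously or barely sized.

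**Working it through.** **Inputs (Statistics section).** Difference 4 mmHg; sigma 1; alpha 0.05; power 1 − 0.2 = 0.80; paired t-test; stated n = 35.

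**Step 1: try to reproduce 35.** For a paired t-test, power comes from the noncentral t distribution with n − 1 degrees of freedom and noncentrality (difference/SD) × √n. Here difference/SD = 4/1 = 4.

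| Reading of the inputs | Result | n |
|---|---|---|
| Paired t, two-sided, sigma = SD of the difference | power 0.343 at n = 2, 0.908 at n = 3 | 3 |
| Paired t, one-sided | power 0.624 at n = 2, 0.991 at n = 3 | 3 |
| Normal approximation, two-sided | (1.960 + 0.842)² / 4² = 7.85/16 = 0.49 | 1 |
| Sigma = SD of one measurement, zero correlation (SD of difference √2, effect 2.83), two-sided | power 0.705 at n = 3, 0.950 at n = 4 | 4 |
| Two independent groups, two-sided t-test | power 0.565 at 2 per group, 0.948 at 3 per group | 6 in total |
| Signed-rank test, two-sided | smallest possible p is 2/2⁵ = 0.0625 with 5 pairs, 2/2⁶ = 0.031 with 6 | at least 6 |

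None comes near 35. The direct reading is out by a factor of 35/3, about 12. A strained reading, with 1 mmHg as the effect (the gap between the 5 mmHg of the further analysis and the 4 mmHg of the power calculation), gives 10 two-sided and 8 one-sided.

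**Step 2: what would give 35?** Solving for 80% power at n = 35:

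- Two-sided: standardised effect 0.487, so SD = 4/0.487 ≈ 8.2 mmHg.
- One-sided: standardised effect 0.429, so SD = 4/0.429 ≈ 9.3 mmHg.

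Neither the effect sizes nor the SDs appear in the document.

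**Step 3: can sigma be 1 mmHg?** Not in the pilot. Among 24 differences that include −16 and +5, the SD is smallest when the other 22 sit at the midpoint. The sum of squares is then 21²/2 = 220.5, and the SD is √(220.5/23) = 3.10 mmHg. This bound assumes no distribution.

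**Step 4: a rough pilot SD.** If the changes are roughly normal, the expected range of 24 values is 3.895 SDs, so SD ≈ 21/3.895 = 5.4 mmHg. The 2.5% and 97.5% quantiles of that range are 2.64 and 5.43 SDs, giving limits of 21/5.43 = 3.9 and 21/2.64 = 8.0 mmHg.

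**Step 5: what 35 infants deliver for 4 mmHg.** Two-sided paired t-test; 95% confidence interval half-width = t(0.975, 34)/√35 × SD = 2.032/5.916 × SD = 0.3435 × SD.

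| SD of paired difference (mmHg) | Basis | Power at n = 35 | n for 80% power | Expected 95% CI half-width (mmHg) |
|---|---|---|---|---|
| 3.9 | lower pilot limit | over 99.9% | 10 | 1.3 |
| 5.4 | pilot range estimate | 99% | 17 | 1.9 |
| 8.0 | upper pilot limit | 82% | 34 | 2.7 |
| 8.2 | SD implied by n = 35 | 80% | 35 | 2.8 |
| 10 | illustration only, beyond the pilot limits | 63% | 52 | 3.4 |

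**Step 6: attrition.** 35/40 = 0.875, an allowance of 12.5%. That step is consistent and not in question.

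**The case against.** The strongest defence is that sigma = 1 was a software entry on a standardised scale. A standardised effect of 0.5 needs 34 infants by two-sided paired t-test, and one near 0.49 needs 35. On this reading the calculation was valid and only the SD that converts 4 mmHg to SD units was left out; it may even stand in the published source cited for the 4 mmHg. This is plausible, but it is inference. It also does not rescue the sentence, because the printed 4 mmHg and sigma = 1 still do not yield 35, and the missing SD is exactly what a reader needs.

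A second argument is that the consequence is small. Every SD within the rough pilot limits of 3.9 to 8.0 mmHg gives at least 82% power at n = 35, so the planned size looks adequate and the defect is one of documentation. The first half stands, subject to the normality assumption and to the pilot resembling the trial. It is why no change to the targets is sought. It does not make the justification correct as written.

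Third, the passage reports a calculation already done, so a new SD put in its place would be a new justification. That is fair, and the fix requires any re-estimate to be labelled as one. The document does not say whether recruitment is complete. If it is, the observed confidence interval will say more about precision than a restated power figure, but the stated basis for the sample size would still need correcting.

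**Conclusion.** The concern holds. The stated inputs give about 3 infants (1 to 6 across the readings tabulated), against a stated 35. Reaching 35 needs an SD of the paired difference of about 8.2 mmHg two-sided or 9.3 mmHg one-sided, and the document reports neither. That sigma cannot be 1 mmHg in the pilot follows from the reported extremes alone.

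The trial is not shown to be underpowered, and 35 or 40 is not shown to be the wrong number. The pilot SD of 5.4 mmHg and its limits assume rough normality, and the SD of 10 mmHg is only an illustration. What is established is that the sole sample-size justification does not follow from its own inputs. It should be corrected before it is relied on.

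**What to change.** 1. Replace sigma = 1 with the SD of the paired pCO₂ difference actually used, in mmHg, with its source and the sidedness of the test.
2. Compare that SD with the SD of the 24 pilot differences, if those are still held. If the SD originally used cannot be documented, use the pilot SD and label it as a later re-estimate. If neither is available, state an assumed SD and show power over a range. Do not back-solve the SD from n = 35.
3. Restate what the sample delivers, for example: *With an SD of paired pCO₂ differences of [X] mmHg ([source]), a two-sided paired t-test at alpha 0.05 with 35 evaluable infants has [Y]% power for a mean change of 4 mmHg; the expected 95% confidence interval half-width is [0.344 × X] mmHg.*
4. If the pilot SD is used, note that the populations differ. The pilot covered "VLBW infants who had increased NAVA support in response to a capillary blood gas were studied", so all were already on NAVA. The trial also admits infants on CPAP, other nasal support or high-flow cannula, and the NAVA settings section treats those already on NAVA as a subgroup, so the trial sample may be only partly on NAVA at entry.

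The cost is one corrected sentence and a look-up of the original calculation or the pilot differences; the document does not say whether either survives. The stated power may move in either direction. No change to 35 or 40 is requested unless the restated figure shows a need.

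### Is the further test for a pCO₂ fall above 5 mmHg a flaw because the trial was sized on 4 mmHg?

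*Combined protocol and SAP*

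**What the plan says.** The Statistics section of the combined protocol and SAP bases the sample size on one effect: "Power calculations were performed using a detectable difference in pre-post pCO₂ of 4mmHg based on published findings". With alpha 0.05, beta 0.2 and sigma 1 it concludes that "the estimated sample size needed to detect a difference is 35 subjects", and it recruits 40 to allow for attrition. The main analysis is a paired t-test of capillary pCO₂ before and after the intervention, against the null of no difference. The next sentence adds the stricter question: "Further analyses will test if the difference is greater than 5mmHg". For that analysis the section states no sidedness, alpha, assumed effect or power. A Wilcoxon signed-rank test is the fallback if the t-test assumptions fail.

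The figure of 5 mmHg also appears under Study Intervention Procedure and Data Collection, as a step in the transcutaneous CO₂ rule: "At 60 minutes of intervention if the TCO₂ average has not decreased by 5 mmHg from baseline" or has risen, the NAVA level is raised. A similar check follows at 90 minutes. The text does not link this rule to the capillary pCO₂ test.

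Under Preliminary Data, 24 infants had a median change of -3.5 mmHg, and "the differences ranged from a decrease of 16 mmHg to an increase of 5 mmHg".

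**The concern.** The threshold of the further test lies above the only effect size used in planning. If the true mean fall is 4 mmHg, the null of the further test (a fall of 5 or less) is true. The chance of a significant result is then below alpha whatever the SD, and it shrinks as more infants are added. The preliminary median of 3.5 mmHg points the same way.

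If so, a result of 'not shown to exceed 5' would be nearly certain before the trial starts. It could be misread as absence of a useful effect, because on its own it does not separate a real fall of about 4 from no fall. The section names no confidence interval that would show the size of the fall.

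**Working it through.** **Inputs.** From the Statistics section: planning difference 4, threshold 5, n = 35 evaluable (40 recruited), alpha 0.05, beta 0.2, sigma 1. Assumptions, because the plan does not give them: the further test is a one-sided t-test on the mean paired change at 0.05, and the SD of the change takes several values.

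**The plan's own figure.** The paired formula is n = (sigma × (z₀.₉₇₅ + z₀.₈₀) / difference)² = (1 × (1.960 + 0.842) / 4)² = 0.49, so 1 infant, or 3 with the exact t calculation. The stated 35 is not reproduced with sigma 1. It needs an SD of the paired change of about 8.2 (two-sided 0.05) or 9.3 (one-sided 0.05). That mismatch is a separate matter. Here it only means that a range of SDs must be used: 1 as stated, 8.2 and 9.3 solved back from n = 35, and 5.4 from the preliminary range. The last is (16 + 5) / 3.89 = 5.4, where 3.89 is the expected range of 24 normal values in SD units.

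**Further test.** The noncentrality is (true fall − 5) × √35 / SD, with 34 degrees of freedom and a one-sided critical value of 1.69. For a true fall of 4 and SD 8.2 it is −1 × 5.916 / 8.2 = −0.72, which gives a rejection probability of 0.9%.

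**Main test on the same data.** The noncentrality is 4 × √35 / SD, two-sided 0.05. For SD 8.2 it is 23.66 / 8.2 = 2.89, which gives power of 80%.

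| SD of change | Further test significant, true fall 4 | Main test against 0 significant, true fall 4 | Further test significant, true fall 7 |
|---|---|---|---|
| 1 | about 0 | about 100% | about 100% |
| 5.4 | 0.3% | 99% | 69% |
| 8.2 | 0.9% | 80% | 41% |
| 9.3 | 1.2% | 70% | 34.5% |

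With n = 40, the first results column becomes 0.3%, 0.8% and 1.0% for the last three SDs.

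**What the columns mean.** The first results column is a false-positive rate. At a true fall of 4, the claim of a fall above 5 is wrong, and the test makes that claim less often than its alpha of 5% allows. That it falls further with more infants is also what a sound test does. The second column answers whether there is any fall, and that analysis is the one the trial was sized for. The third shows that the further test can succeed when the claim is true; 7 is only an illustration.

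**Reading the two results together.** Significant against 0 but not against 5 means a fall was shown, but not one above 5. Significant against both means a fall above 5 was shown. Not significant against 0 means no fall was shown. The plan as written gives all three readings.

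**The case for a change.** The strongest case is that the plan never assumes a fall for which the 5 mmHg test would be informative, so the yes/no answer adds little near 4. A 95% confidence interval would say more. At a true fall of 4 it would exclude 0 yet include 5 in 81%, 79% or 69% of trials (SD 5.4, 8.2, 9.3), and in those trials a careless reader could take the missed threshold for lack of effect.

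Some of this stands. An interval would be good reporting, and the sidedness and alpha of the further test should be settled before the data are analysed. Neither omission makes a conclusion wrong:

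- The misreading requires ignoring the main result, which tests against zero and is reported alongside. The planned figures of starting against final pCO₂ and of the distribution of the change also show the size of the fall.
- The plan calls 4 mmHg a detectable difference. That is a sizing value, not a forecast. The study procedure itself uses a 5 mmHg fall in transcutaneous CO₂ as its step, so asking whether capillary pCO₂ fell by more than 5 is not a stray question. It is true that the plan states no larger expected fall either.
- A further analysis need not be powered, and none of the plan's power figures is attached to this one.
- Putting a two-sided 95% interval in place of the test would make the same comparison with 5 at one-sided 0.025. Power at a true fall of 7 would drop from 69% to 57% (SD 5.4) and from 41% to 29% (SD 8.2). That is a trade-off on which reasonable statisticians differ.

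**Conclusion.** No error. The further test asks a stricter question than the main one, and it rarely gives a positive answer at a true fall of 4 because the correct answer there is no. Its rejection rate of about 0 to 1.2% (n = 35, one-sided 0.05, SD 1 to 9.3) shows valid behaviour. The main test against zero is unaffected and has two-sided power of about 70% to 99% at SD 9.3 to 5.4.

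These percentages rest on SDs that the plan does not give, apart from sigma 1, and on reading the sentence as a one-sided test of the mean change. The conclusion does not depend on the choice of SD: a true fall of 4 lies inside the null of this test for every SD. Stating sidedness and alpha and adding an interval would be tidy, but following the plan as written leads to sound conclusions.
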